## 2.8.4 Other safety data

### 2.8.4.1 ECG and cardiac imaging data

#### ECG Data handling

In case the study requires ECG replicates at any assessment, the average of the ECG parameters at that assessment should be used in the analyses.

#### ECG Data analysis

The number and percentage of patients with notable ECG values at scheduled assessments will be presented by Parts A, B, C, and D.

- QTcB
  - New value of  $> 450$  and  $\leq 480$  ms
  - New value of  $> 480$  and  $\leq 500$  ms
  - New value of  $> 500$  ms
  - Increase from Baseline of  $> 30$  ms to  $\leq 60$ ms
  - Increase from Baseline of  $> 60$  ms
- PR
  - Increase from baseline  $>25\%$  and to a value  $> 200$  ms
  - New value of  $> 200$  ms
- QRS
  - Increase from baseline  $>25\%$  and to a value  $> 120$  ms
  - New values of QRS  $> 120$  ms

The normal range for HR is displayed in [Table 2-7 Recommendation for normal heart rate per age group and gender](#). The number and percentage of patients with notable values will be presented.

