### **Windows for multiple assessments**

In order to summarize (vital sign, performance status, etc.) data collected over time (including unscheduled visits), the assessments will be time slotted. The following general rule will be applied in creating the assessment windows: If more than one assessment is done within the same time window, the assessment performed closest to the target date will be used. If 2 assessments within a time window are equidistant from the target date, then the worse of 2 assessments (i.e. farthest outside the normal range) will be used. If multiple assessment are on the same date then the worst case will be used. Data from all assessments (scheduled and unscheduled), including multiple assessments, will be listed.

For all analyses regarding abnormal assessments or analyses based on worst or best post-baseline value (laboratory, ECGs, vital signs, Karnofsky/Lansky performance status, ECHO etc.), all post-baseline values will be included (scheduled, unscheduled, repeat).

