**Table 2-7 Recommendation for normal heart rate per age group and gender**

Age group	0-1 month	1-3 months	3-6 months	6-12 months	1-3 years	3-5 years	5-8 years	8-12 years	12-18 years
HR (bpm) Boys	(125, 190)	(125, 185)	(110, 165)	(105, 165)	(95, 155)	(75, 125)	(60, 115)	(55, 100)	(50, 100)
HR (bpm) Girls	(135, 215)	(125, 200)	(120, 190)	(105, 185)	(95, 180)	(80, 125)	(70, 115)	(60, 110)	(50, 100)

Data shown as upper limit of normal, lower limit of normal for HR= heart rate. Ref.: adapted from Rijnbeek et al. 2001.

The summaries will include all ECG assessments performed no later than 30 days after the last date of study drug. A listing of all ECG assessments will be provided and notable values will

be flagged. In the listing, the assessments collected outside of on-treatment period will be flagged.

The denominator to calculate percentages for each category is the number of patients with both a baseline and a post-baseline evaluation. A newly occurring post-baseline ECG notable value is defined as a post-baseline value that meets the criterion post-baseline but did not meet the criterion at baseline.

For each of the ECG parameter, descriptive statistics at baseline, at each post-baseline time point and changes from baseline at each post-baseline time point will be summarized. Descriptive statistics at worst post-baseline and changes from baseline to worst post-baseline will also be summarized separately. For each of the QTcB and QT intervals, shift tables based on notable parameter categories (<450, 450-<481, 481-<501, ≥501 ms) at baseline and the worst post-baseline value observed.

Patients with notable ECG interval values and newly occurring qualitative ECG abnormalities will be listed and the corresponding notable values and abnormality findings will be included in the listings.

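### The notable-ECG table is worded for scheduled assessments only, which conflicts with the SAP's general rule and can lower the reported percentages

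*SAP*

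**What the plan says.** Three pieces of SAP text bear on which ECGs enter the notable-value table.

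- **The table itself (section 2.8.4.1, ECG Data analysis).** The opening sentence reads: "The number and percentage of patients with notable ECG values at scheduled assessments will be presented by Parts A, B, C, and D". The criteria that follow are absolute and change categories for QTcB, and new values and percentage increases for PR and QRS.
- **The general rule (section 2.1.1, Windows for multiple assessments).** "For all analyses regarding abnormal assessments or analyses based on worst or best post-baseline value (laboratory, ECGs, vital signs" and other named data types), the rule is that "all post-baseline values will be included (scheduled, unscheduled, repeat").
- **The text after Table 2-7 in the same ECG section.** "The summaries will include all ECG assessments performed no later than 30 days after the last date of study drug". A newly occurring notable value is a "post-baseline value that meets the criterion post-baseline but did not meet the criterion at baseline". The denominator for each category "is the number of patients with both a baseline and a post-baseline evaluation". Neither definition is confined to scheduled visits.

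The same section also provides other ECG displays. On worst values: "Descriptive statistics at worst post-baseline and changes from baseline to worst post-baseline will also be summarized separately". The QTcB and QT shift tables compare categories "at baseline and the worst post-baseline value observed". All ECGs are listed with notable values flagged, and patients with notable intervals have their own listing.

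**The concern.** A count of patients with a notable ECG value is plainly an analysis of abnormal assessments, so the general rule in section 2.1.1 covers it. The ECG section nevertheless restricts the count to scheduled assessments. Two programmers could each follow the SAP and build different tables.

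The choice matters for two reasons. ECG is part of the primary endpoint for Parts A to D (section 2.5.1). No hypothesis is tested in any part (section 2.5.2), so the descriptive counts are themselves the reported result. If unscheduled tracings are left out of the numerator, the table can under-report the very values it is meant to show.

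**Working it through.** The SAP gives no figure to reproduce here: no number of unscheduled ECGs and no expected rate of notable values. The check is a comparison of text, followed by simple arithmetic on what one patient would weigh.

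**1. Which ECGs can enter the numerator**

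| Source | ECGs admitted |
|---|---|
| Section 2.8.4.1, table sentence | scheduled only |
| Section 2.1.1, general rule | scheduled, unscheduled, repeat |
| Section 2.8.4.1, definition of a new notable value | any post-baseline value that qualifies |

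The first row conflicts directly with the second and fits poorly with the third. Section 2.1.1 has no clause letting a later section override it, and section 4 (changes to protocol-specified analyses) does not address the point.

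**2. Which patients enter the denominator**

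The denominator needs a baseline and a post-baseline evaluation, with no condition that the latter be scheduled.

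**3. Direction**

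Let *n* be the denominator, *s* the patients with a notable value at a scheduled ECG, and *u* the patients whose only notable value was at an unscheduled or repeat ECG.

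- Table sentence followed: *s*/*n*
- General rule followed: (*s* + *u*)/*n*
- Difference: *u*/*n*, which is zero or positive

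So the scheduled-only percentage is never higher. This follows from the definitions and needs no assumption about why unscheduled ECGs are done.

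**4. Weight of one patient (*u* = 1), from the planned sizes in section 3**

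| Group | *n* | 1/*n* |
|---|---|---|
| Part A | about 48 | 2.1 points |
| Part B | at least 40 | 2.5 points |
| Part C | about 18 | 5.6 points |
| Part D | at least 30 | 3.3 points |
| Disease cohort of 20 | 20 | 5 points |
| Disease cohort of 10 | 10 | 10 points |

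The table sentence presents results by Part, so the first four rows apply to it. The last two apply because section 2.8 also summarizes ECG data by disease cohort. If the 6 subjects of the Part C extension (section 1.1) are additional to the 18, Part C has 24 and one patient weighs 1/24 = 4.2 points.

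**5. What the other displays cover**

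Through the general rule, unscheduled ECGs reach the worst post-baseline statistics for every ECG parameter and the shift tables. The shift tables cover only absolute QTcB and QT bands. For new PR values above 200 ms, new QRS values above 120 ms, the increases of more than 25% in PR and QRS, and the QTcB increases of more than 30 to 60 ms and of more than 60 ms, the notable-value table is the only patient count specified in the ECG section.

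Where the displays overlap, they could disagree. Take a patient with a normal baseline whose only QTcB of 510 ms was at an unscheduled ECG. That patient would sit in the top shift band but be missing from the count of new values above 500 ms.

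**The case against.** The strongest reply is that the SAP, read as a whole, already favours counting every ECG. The general rule names ECGs, and the definition of a new notable value and the denominator are both unrestricted. On that view the scheduled-only phrase is a slip that a programmer would probably resolve correctly. This stands in part: the text is ambiguous, and no undercount occurs if the general rule is applied. But nothing in the SAP settles the matter, and the most specific sentence points the other way.

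The sentence about ECGs up to 30 days after the last dose adds little to the conflict. It reads mainly as a time cut-off, and similar wording is used for laboratory and ECHO data. The firm contradiction is with section 2.1.1.

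A reader might also infer more than the SAP supports, in three ways.

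- *That unscheduled ECGs drop out of the primary safety endpoint.* They do not. They stay in the worst-value statistics, the QTcB and QT shift tables and the listings. Only one set of patient counts is at issue.
- *That an undercount is certain.* It occurs only if the table sentence is followed and at least one patient had a notable value solely at an unscheduled ECG.
- *That unscheduled ECGs are those prompted by a clinical concern, and so the likeliest to be abnormal.* This is plausible, but the SAP does not say it.

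**Conclusion.** The inconsistency is real and should be resolved, but its reach is narrow. If the table sentence governs, the notable-value percentages are equal to or below those under the general rule, by *u*/*n*. The SAP does not give *u*, which may be zero, so the actual effect is unknown. The per-patient weights rest on planned enrolment and assume that every enrolled patient has a baseline and a post-baseline ECG; a smaller evaluable denominator would make each patient weigh more. The practical exposure is mainly the PR, QRS and QTcB-increase categories. No decision rule in the visible text depends on these counts.

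**What to change.** In section 2.8.4.1, replace the scheduled-assessment restriction with: *at any post-baseline on-treatment assessment (scheduled, unscheduled or repeat)*. Keep scheduled visits, under the assessment-window rule of section 2.1.1, only for the descriptive statistics by time point. The denominator and the definition of a new notable value then fit without further change.

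The cost is one phrase in the SAP and one filter in one table, to be settled before database lock. The reported rates may be slightly less favourable.

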### 1.1 Study design

This is a 4-part (Part A, Part B, Part C and Part D), Phase I/IIa, multi-center, open label, study in pediatric subjects with refractory or recurrent tumors.

**Part A** will be a pharmacokinetically driven limited dose escalation (i.e., 0.0125, 0.025 and 0.04 mg/kg/day) in subjects and will include an expansion for safety, tolerability, and pharmacokinetics (PK) in three age ranges (1 month to <2years, 2 to ≤12 years, and over 12 years of age). The primary goal of Part A is to establish the toxicity profile, PK, and recommended Phase 2 dose (RP2D) of trametinib in each age cohort. Approximately 18 subjects will be accrued to the dose escalation phase and 18 subjects to the age expansion phase.

**Part A extension** will be an age-specific dose exploration in up to 12 subjects aged 1 month to < 6 years old. Preliminary PK analysis of pediatric patients in this current study suggests that for patients < 6 years old, an intermediate dose (i.e., 0.032 mg/kg/day) may increase the proportion of these patients who achieves exposures similar to adults. The goal of this additional dose exploration is to establish the safety, tolerability, PK and further refine the RP2D of trametinib in this younger age cohort.

**Part B** will be a tumor cohort expansion part of the study to further evaluate the safety, tolerability, and preliminary clinical activity of trametinib at the dose determined in Part A in tumor-specific pediatric populations. Disease cohorts are selected based on current data of proto-oncogene RAS (Ras)/ mitogen-activated protein kinase (MAPK) activation in childhood solid tumors. At least forty subjects are planned for Part B, 10 subjects in each of 4 disease cohorts.

- B1: Refractory or relapsed neuroblastoma
- B2: Recurrent or unresectable low grade gliomas associated with BRAF tandem duplication with fusion, or NF-1 subjects with gliomas, not suitable for the NF-1 with PN cohort
- B3: Neurofibromatosis Type -1 associated plexiform neurofibromas that are unresectable and medically significant.

- B4:BRAF V600 mutant tumors

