**Part C** will be a limited dose escalation part of the study evaluating the combination of trametinib with dabrafenib in children and adolescents with recurrent, refractory or unresectable BRAF V600 mutated tumors. This part of the study will establish recommended Phase 2 doses (RP2D) of dabrafenib and trametinib when given in combination in children and adolescents. This part of the study will enroll approximately 18 subjects (including up to 6 adolescent subjects with BRAF V600 mutant metastatic melanoma) and will not open to accrual until the dose of dabrafenib in children is established in study BRF116013, the dose of trametinib is established in Part A and review of the available safety and PK data of trametinib and dabrafenib monotherapy in children is completed. Amendment 3 provides the updated safety data and dabrafenib dosing in children. Parts B and C may be open to accrual simultaneously. Patients who have had prior dabrafenib therapy may enroll in part C if they have had prior benefit to dabrafenib monotherapy, as determined by the investigator.

**Part C extension** will be an age-specific dose exploration in 6 subjects aged 12 months to < 6 years old. If the trametinib dose of 0.032 mg/kg/day is tolerated in Part A extension, a combination of trametinib 0.032mg/kg/day and the full dabrafenib pediatric RP2D will be tested in this cohort. The goal of this additional dose exploration is to establish the safety, tolerability, PK and RP2D of the trametinib and dabrafenib combination in this younger age cohort

**Part D** will be a tumor cohort expansion part of the study to further evaluate the safety, tolerability, and preliminary clinical activity of the combination of trametinib and dabrafenib in tumor-specific pediatric populations listed below.

- D1: BRAF V600-mutant, relapsed or refractory low grade glioma (LGG)
- D2: BRAF V600-mutant, relapsed or refractory Langerhans cell histiocytosis (LCH)

Disease cohorts are selected based on current data of proto-oncogene RAS (Ras)/ mitogen-activated protein kinase (MAPK) activation in childhood solid tumors. Pediatric subjects 12 months to < 18 years of age are to be enrolled. Approximately 20 subjects with LGG and 10 subjects with LCH will be enrolled.

Subjects may not enroll in more than one part of the study. Subjects will receive study treatment until disease progression, death or unacceptable toxicity.

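### Corrected QT is analysed by Bazett alone with fixed cut-offs from 1 month to 18 years, so heart-rate changes on treatment could move children into or out of the QTcB categories, with no second correction to show it

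*SAP*

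**What the plan says.** ECG is one component of the primary endpoint for every study part (SAP 2.5.1). In 2.8.4.1 the notable corrected-QT values are all defined on QTcB. There are three bands of new absolute values, the highest being "New value of $> 500$ ms", and two bands of change, >60 ms and "Increase from Baseline of $> 30$ ms to $\leq 60$ ms". None varies with age.

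The text after Table 2-7 adds three things:
- Shift tables, in these words: "For each of the QTcB and QT intervals, shift tables based on notable parameter categories". The QTcB and uncorrected QT tables share cut-points of 450, 481 and 501 ms and compare baseline with the worst post-baseline value.
- Descriptive summaries: "For each of the ECG parameter, descriptive statistics at baseline, at each post-baseline time point and changes from baseline", plus separate summaries at the worst post-baseline value.
- A rule that a value is new only if the criterion was not already met at baseline.

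Heart rate is judged by age and sex ("The normal range for HR is displayed in" Table 2-7), in its own tabulation. Part A enrols "three age ranges (1 month to <2years, 2 to ≤12 years, and over 12 years of age"; for Part D, "Pediatric subjects 12 months to < 18 years of age are to be enrolled". Section 2.1.1 brings scheduled, unscheduled and repeat ECGs into any worst-value analysis. The SAP names no other QT correction and no QT-RR model.

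**The concern.** Bazett's correction divides QT by the square root of RR. It removes the effect of heart rate only if QT really varies with that power of RR. If the true power is smaller, QTcB over-corrects at fast rates and rises with heart rate.

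The plan treats heart rate as strongly age-dependent when it sets heart-rate norms, yet uses one set of QTcB cut-offs throughout and has no check on rate dependence. Two kinds of error could follow in a primary-endpoint component:
- **False signals.** A child whose heart rate is higher at a post-baseline ECG than at baseline, for instance during fever, could enter a change category with no change in repolarisation.
- **Masked signals.** A child already above 450 ms at baseline because of a fast rate cannot become a new case above 450 ms. A heart rate that falls with growth during long treatment would lower QTcB and offset a real prolongation.

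**Working it through.** **Inputs.** QTcB is read as Bazett's correction. The cut-offs come from SAP 2.8.4.1. Heart rates come from Table 2-7: 50-100 bpm at 12-18 years (both sexes); 95-155 (boys) and 95-180 (girls) at 1-3 years; 125-200 for girls of 1-3 months. The whole-table maximum is 215 bpm, in girls of 0-1 month, but Part A starts at 1 month. The table footnote reads "Data shown as upper limit of normal, lower limit of normal for HR= heart rate", while the pairs run from low to high. They are read here as lower, upper.

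**Assumptions.** The SAP gives neither the true QT-RR exponent b nor a reference QTc. True QTc is held at 400 ms and b is varied from 1/3 (the cube-root, Fridericia value) to 0.55.

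**Formula.** With RR = 60/HR, QTcB = QT/RR^0.5. If QT = QTc_true × RR^b, then QTcB = QTc_true × (HR/60)^(0.5 − b).

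**Level at b = 1/3.** QTcB = 400 × (HR/60)^(1/6): 388 ms at 50 bpm, 436 at 100, 452 at 125, 469 at 155, 480 at 180 and 489 at 200. The 450 ms line is crossed at 60 × (450/400)^6 ≈ 122 bpm and the 480 ms line at 60 × (480/400)^6 ≈ 179 bpm. The 500 ms line would need about 229 bpm, beyond any rate in the table. At b = 0.40 the 450 ms line is crossed only at 60 × (450/400)^10 ≈ 195 bpm.

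**Change within one child, true QTc constant** (ms, differences taken before rounding):

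| b | 95→155 bpm | 95→180 bpm | 50→100 bpm | 155→125 bpm |
|---|---|---|---|---|
| 1/3 | +36.7 | +48.5 | +47.5 | −16.5 |
| 0.40 | +21.0 | +27.6 | +28.2 | −9.4 |
| 0.45 | +10.1 | +13.3 | +14.0 | −4.5 |
| 0.50 | 0 | 0 | 0 | 0 |
| 0.55 | −9.5 | −12.3 | −13.8 | +4.1 |

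The three rises each run from the bottom to the top of one normal band. At b = 1/3 all fall in the >30 to ≤60 ms category; at 0.40 none does. From 95 bpm at b = 1/3, an increase of 30 ms needs about 142 bpm. An increase of 60 ms needs about 207 bpm, above the 1-3 year range. A milder rise, from 100 to 130 bpm, adds 19.5 ms at b = 1/3 and meets no change criterion.

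**Does the uncorrected QT table help?** At 125 bpm, RR = 60/125 = 0.48 s. A QT of 450 ms then means QTcB = 450/0.48^0.5 ≈ 650 ms, or a cube-root value of 450/0.48^(1/3) ≈ 575 ms. With cut-points starting at 450 ms, that table can hardly register prolongation at fast rates.

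**The case against.** The QTcB categories are explicit, reproducible and free of contradiction, and the protocol, which was not part of this review, may prescribe QTcB. The heart-rate effect depends wholly on an exponent that the SAP does not give: it vanishes at 0.50, reverses at 0.55, and at 0.40 does not reach 30 ms even over a full normal band. If the true exponent is near 0.5, the cube-root correction is the biased one. All of this stands, and it rules out saying that QTcB is wrong or that QTcF is right.

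A reader might also infer that QTcB differences between cohorts are largely an artefact of age mix. The documents do not support that. The new-value rule and the shift from baseline remove much of a constant age-related offset: a toddler above 450 ms at baseline because of a stable fast rate is not counted as a new case.

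Those rules do not deal with a heart rate that changes on treatment, and the new-value rule itself creates the masking at baseline. Nor do they stop worst-value summaries over all ECGs from favouring fast-rate recordings if QTcB over-corrects.

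Finally, heart rate has its own summaries and all ECGs are listed with notable values flagged, so a reader could look for a rate change. But the plan does not tie heart rate to the QTcB counts.

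**Conclusion.** The point holds in a conditional form, as a moderate weakness in the choice of analysis and not as an error or contradiction. The SAP relies on one correction with fixed cut-offs across a very wide range of normal heart rates and plans nothing to show whether the result depends on that choice.

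The size rests on the assumed exponent and the 400 ms reference. A 95 to 155 bpm rise adds about 37 ms at 1/3, 21 ms at 0.40, 10 ms at 0.45 and 0 at 0.50. Within the normal bands worked above, only the >30 to ≤60 ms change category is reachable by heart rate alone, and only at the lower end of the exponent range. In absolute terms, the 450 ms line and, at the fastest rates, the 480 ms line are reachable at b = 1/3. The highest rates concern infants; Part D starts at 12 months, where the upper normal limit is 180 bpm. The documents do not establish that any count will in fact be distorted.

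**What to change.** Keep every QTcB analysis as planned. Add to 2.8.4.1:
- Derive QTcF for each ECG from the recorded QT and heart rate.
- Repeat the notable-value, change-from-baseline and shift tables with QTcF, labelled as a sensitivity summary and with no claim that QTcF is the correct reference.
- In the listing, show heart rate at baseline and at the event beside each flagged QTcB value.

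The cost is SAP wording before database lock, one derived variable, repeat tables and extra listing columns; no new data are needed. The drawback is a second set of ECG tables that may disagree with the first. Such a disagreement would show that the finding depends on the correction, and the listed heart rates would help to interpret it.

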**Table 2-7 Recommendation for normal heart rate per age group and gender**

Age group	0-1 month	1-3 months	3-6 months	6-12 months	1-3 years	3-5 years	5-8 years	8-12 years	12-18 years
HR (bpm) Boys	(125, 190)	(125, 185)	(110, 165)	(105, 165)	(95, 155)	(75, 125)	(60, 115)	(55, 100)	(50, 100)
HR (bpm) Girls	(135, 215)	(125, 200)	(120, 190)	(105, 185)	(95, 180)	(80, 125)	(70, 115)	(60, 110)	(50, 100)

Data shown as upper limit of normal, lower limit of normal for HR= heart rate. Ref.: adapted from Rijnbeek et al. 2001.

The summaries will include all ECG assessments performed no later than 30 days after the last date of study drug. A listing of all ECG assessments will be provided and notable values will

be flagged. In the listing, the assessments collected outside of on-treatment period will be flagged.

The denominator to calculate percentages for each category is the number of patients with both a baseline and a post-baseline evaluation. A newly occurring post-baseline ECG notable value is defined as a post-baseline value that meets the criterion post-baseline but did not meet the criterion at baseline.

For each of the ECG parameter, descriptive statistics at baseline, at each post-baseline time point and changes from baseline at each post-baseline time point will be summarized. Descriptive statistics at worst post-baseline and changes from baseline to worst post-baseline will also be summarized separately. For each of the QTcB and QT intervals, shift tables based on notable parameter categories (<450, 450-<481, 481-<501, ≥501 ms) at baseline and the worst post-baseline value observed.

Patients with notable ECG interval values and newly occurring qualitative ECG abnormalities will be listed and the corresponding notable values and abnormality findings will be included in the listings.

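### SAP Section 2.8.4.1: the rule for new ECG values, applied to closed QTcB bands, can count a fall in QTcB as a new notable value; the QT shift-table cut-offs need aligning

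*SAP*

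**What the plan says.** All the relevant text is in SAP Section 2.8.4.1.

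- **Notable QTcB rows.** There are three for new values: "New value of $> 450$ and $\leq 480$ ms", "New value of $> 480$ and $\leq 500$ ms" and "New value of $> 500$ ms". Two further rows cover increases from baseline of more than 30 up to 60 ms, and of more than 60 ms. The PR and QRS rows use single open thresholds.
- **Meaning of new.** After Table 2-7, a newly occurring notable value is "a post-baseline value that meets the criterion post-baseline but did not meet the criterion at baseline".
- **Denominator.** "The denominator to calculate percentages for each category is the number of patients with both a baseline and a post-baseline evaluation". Children already above a threshold at baseline stay in.
- **Shift table.** The SAP specifies "shift tables based on notable parameter categories (<450, 450-<481, 481-<501, ≥501 ms"), and the same categories serve both intervals: "For each of the QTcB and QT intervals".
- **Replicates.** If replicate ECGs are required, their average is analysed.

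The ECG data analysis text presents notable values by Part. Section 2.8 also asks for ECG summaries by dose level and disease cohort. Section 2.5.1 names ECG among the primary endpoints of every Part.

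**The concern.** The definition of new works for an open threshold. A value above 500 ms that was not above 500 ms at baseline must have risen. It does not work for a closed band, because a patient can be outside the band at baseline by lying above it. Entry from above then counts the same as entry from below, so an improvement can be reported as a new abnormality in a primary safety endpoint.

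Two smaller points sit beside this. The shift table uses slightly different boundaries for the same measure, so one value can be classified differently in two tables. The shift categories are also applied to uncorrected QT, although their meaning there depends on heart rate.

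**Working it through.** The SAP gives no figure on this point, so there is none to reproduce. The rules were applied as written.

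**1. The new-value rule.** A value is flagged in a band if the post-baseline value lies in it and the baseline value does not.

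| Baseline (ms) | Post-baseline (ms) | Change | Flagged as new in |
|---|---|---|---|
| 490 | 470 | -20 | >450 to 480 |
| 510 | 495 | -15 | >480 to 500 |
| 510 | 470 | -40 | >450 to 480 |
| 440 | 470 | +30 | >450 to 480 |
| 490 | 510 | +20 | >500 |

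Take all whole-millisecond pairs from 400 to 560 ms in which QTcB falls. The flagged pairs are:

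- baseline 481–500, later 451–480: 20 × 30 = 600
- baseline 501–560, later 451–480: 60 × 30 = 1,800
- baseline 501–560, later 481–500: 60 × 20 = 1,200

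The total is 3,600. Every one has baseline above 480 ms and none falls in the >500 ms row. This count shows where the rule fails. It is not an estimate of how often.

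**2. Size of one false case.** Planned numbers are from SAP Section 3.

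- Part A, about 48: 1/48 = 2.1 points
- Part B, at least 40: 1/40 = 2.5 points
- Part C, about 18: 1/18 = 5.6 points
- Part D, at least 30: 1/30 = 3.3 points
- A disease cohort of 10: 1/10 = 10 points

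**3. Boundaries.** The notable rows imply ≤450, >450–480, >480–500 and >500. Against the shift categories, whole-millisecond values differ only at exactly 450 ms, which is not notable but falls in the second shift category. Averaged values also differ between 480 and 481 and between 500 and 501. For example, 500.67 ms is above 500 in one table and in 481–<501 in the other.

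**4. Uncorrected QT.** The SAP names QTcB but prints no formula, so Bazett is assumed: QT = QTcB × √(60/HR). Heart rates are from Table 2-7.

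- Boys aged 1–3 years, 95 bpm: 500 × √(60/95) = 397 ms
- Boys aged 1–3 years, 155 bpm: 500 × √(60/155) = 311 ms
- QT of 450 ms at 95 bpm: QTcB = 450/√(60/95) = 566 ms
- Age 12–18 years, 50 bpm: QT of 450 ms gives QTcB = 450/√(60/50) = 411 ms
- Two scales equal: √(60/HR) = 1, so HR = 60 bpm
- QTcB of 500 ms reaches QT of 450 ms when √(60/HR) = 0.9, so HR is about 74 bpm

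A QTcB of 500 ms in a young child at these rates is therefore binned as <450. A QTcB of about 411 ms in an adolescent at 50 bpm enters a raised bin.

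**The case against.** The strongest reply is that the practical effect may be nil. The error needs a baseline QTcB above 480 ms. The SAP gives no count of such children, and the eligibility criteria are in the protocol, which is not shown. This stands, and it limits the size of the point.

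The counting rule is also open. The ECG text speaks of scheduled assessments, while the paragraph on windows for multiple assessments in Section 2.1.1 includes all post-baseline values when abnormality is analysed. Neither says whether a patient is counted in every band reached or only by worst value. A reader might infer that every child starting above 480 ms with any later value in a lower raised band becomes a false case. The SAP does not establish that. Under worst-value counting, a child going from 490 to 495 and later 470 ms is not flagged. A child whose worst later value is 470 ms still is, so the defect survives either reading.

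Other outputs help. The baseline-to-worst shift table, the change-from-baseline summaries and the listing would show that such a child improved. They do not correct the count of new values. The analysis is descriptive with no hypothesis tested (Section 2.5.2), which limits the consequence.

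A reader might also infer that the QT shift table cannot detect prolongation. That is too strong. Under Bazett, a QTcB of 500 ms reaches the 450 ms cut-off at rates up to about 74 bpm, and Table 2-7 includes such rates as normal from age 5 years. The SAP also requires the same table for QTcB, so a signal missed on QT is not hidden overall.

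**Conclusion.** The point holds within limits. As written, the new-value rule can report a fall in QTcB as a new notable value in the two closed bands, for children with baseline QTcB above 480 ms, and nothing else in the SAP corrects that count. One such case moves a by-Part percentage by about 2 to 6 points at the planned sizes. The 10-point figure applies only to a cohort of 10 and should not be read across to the by-Part tables. How many cases will occur cannot be determined from the SAP.

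The boundary mismatch is real but narrow: exactly 450 ms, plus two 1-ms gaps that matter only if averaged or otherwise fractional values occur. The use of QTc categories for uncorrected QT is a matter of interpretation. If QTcB is Bazett-corrected, the table under-detects at the faster rates of young children and over-flags at slow adolescent rates. Both are secondary to the new-value rule.

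**What to change.** 1. Replace the closed bands for new values with cumulative thresholds (>450, >480 and >500 ms), each counted only when baseline is at or below that threshold. A flagged value must then exceed baseline, so no improvement can be counted. If the bands are kept, classify each patient once by worst post-baseline value and require a higher band than at baseline. A third wording, which keeps the bands and requires baseline at or below the band's lower limit, was checked on the 400–560 ms grid. The 3,600 falsely flagged pairs dropped to 0 and every rise flagged before stayed flagged.
2. Use the boundaries of the notable rows in the QTcB shift table: ≤450, >450–480, >480–500 and >500 ms.
3. Restrict that categorical shift table to QTcB. The descriptive summaries already planned for each ECG parameter can cover uncorrected QT.

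The cost is a few lines of SAP text and a small programming change. No new data are needed.
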